#### **PRECIS**

PRECIS total score and domain scores will be calculated as averages of their constituting non-missing items. Table 6.6:1 lists the minimum number of non-missing items required for calculation of PRECIS total score and domain scores. If fewer items than the minimum requirement are non-missing, the corresponding total score or domain score will not be calculated and will be treated as missing.

Table 6.6: 1 PRECIS minimum non-missing items required for total/domain score calculation

		Minimum required non-missing items
		PRECIS (28-item version)
	Memory	3 out of 6
	Communication	3 out of 4
Domain	Self-Control	3 out of 3
Don	Executive Function	4 out of 4
	Attention	3 out of 6
	Sharp Thinking	3 out of 3
PRE	CIS total score	19 out of 26

#### 6.7 BASELINE, TIME WINDOWS AND CALCULATED VISITS

In general, baseline values are the measurements taken prior to the first administration of trial medication. For assessments of efficacy, and C-SSRS, baseline will be defined as the last available assessment performed at or before randomization (Visit 2), and no later than the day of the first administration of study medication. Assessments done at Visit 1 or Visit 1a can be used as baseline if Visit 2 assessment is not planned, not available, or invalid.

For MCCB, only the assessment performed at randomization (Visit 2), and no later than the day of the first administration of study medication will be used as the baseline. If no valid assessment is available at Visit 2 then baseline value will be missing; assessments performed at Visits 1 and 1a will not be used as baseline.

Tables in this section define the analysis visits and windows which will be used for the analyses of efficacy and safety endpoints. Actual study day will be calculated starting with the date of first administration of trial treatment as Day 1. Unscheduled assessments will be mapped to the analysis visits together with the scheduled assessments.

Inclusion of an assessment into mapping consideration will depend on its on-/off-treatment status and per specific estimand (i.e., off-treatment data will be included into mapping consideration only when the associated ICE is handled under the treatment policy approach). If more than one assessment falls into the same analysis visit window, the assessment

performed closest to the planned day will be selected for analyses. In case of a tie, the later assessment will be used.

Table 6.7: 1 Analysis visit windows for MCCB, VRFCAT, SCoRS,

Analysis Visit	Nominal Week	Planned Day	Actual Day Window
Baseline		1	≤1
Visit 6	Week 12	85	2 – 126
Visit 11	Week 26	183	≥127

Table 6.7: 2 Analysis visit windows for PRECIS,

Analysis Visit	Nominal Week	Planned Day	Actual Day Window
Baseline		1	≤1
Visit 7	Week 15	106	2 – 126
Visit 10	Week 24	169	≥127

Table 6.7: 3 Analysis visit windows for Tower of London,

Analysis Visit	Nominal Week	Planned Day	Actual Day Window
Baseline		1	≤1
Visit 11	Week 26	183	≥2
(for Tower of London,			

[figure not shown]

Table 6.7: 7 Analysis visit windows for clinical laboratory evaluations (on-treatment period)

Analysis Visit	Nominal Week	Planned Day	Actual Day Window
Baseline		1	≤1
Visit 2	Week 0 (post-baseline)	1	2 – 35
Visit 4	Week 6	43	36 – 77
Visit 6	Week 12	85	78 – 119
Visit 8	Week 18	127	120 – 140
Visit 9	Week 21	148	141 – 161
Visit 10	Week 24	169	162 – 175
Visit 11	Week 26	183	≥176

All post-baseline actual day windows will be curtained at the end of residual period if earlier than the specified upper bound in the table.

Table 6.7: 8 Analysis visit windows for weight and vital signs (on-treatment period)

Analysis Visit	Nominal Week	Planned Day	Actual Day Window
Baseline		1	≤1
Visit 2	Week 0 (post-baseline)	1	2 – 56
Visit 5	Week 9	64	57 – 119
Visit 8	Week 18	127	120–175
Visit 11	Week 26	183	≥176

All post-baseline actual day windows will be curtained at the end of residual period if earlier than the specified upper bound in the table.

[figure not shown]
Table 6.7: 9 Analysis visit windows for clinical laboratory evaluations, weight, and vital signs (post-treatment period)

Analysis Visit	Nominal Week	Planned Day	Actual Day Window (days after last dose)
Follow-up 2	14 days post-treatment	EOT + 14 days	13 – 19
Follow-up 4	21 days post-treatment	EOT + 21 days	20 – 26
Follow-up 6	28 days post-treatment	EOT + 28 days	>27

This analysis visit windows only apply to the post-treatment period defined in Table 6.1: 2

Table 6.7: 10 Analysis visit windows for PWC-20

Analysis Visit	Nominal Week	Planned Day	Actual Day Window (days after last dose)
Last value on treatment			<7
Follow-up 1	7 days post-treatment	EOT + 7 days	7 – 13
Follow-up 2	14 days post-treatment	EOT + 14 days	14 – 16
Follow-up 3	17 days post-treatment	EOT + 17 days	17 – 20
Follow-up 4	21 days post-treatment	EOT + 21 days	21 – 23
Follow-up 5	24 days post-treatment	EOT + 24 days	24 – 27
Follow-up 6	28 days post-treatment	EOT + 28 days	28 – 41
Post safety follow up			≥42

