3.3.3 Exclusion criteria

- 1. Patient with current DSM-5 diagnosis other than Schizophrenia, including but not limited to bipolar, schizoaffective, major depressive disorder etc. The Mini-International Neuropsychiatric Interview (M.I.N.I.) for psychotic disorders should be used for guidance.
- 2. Cognitive impairment due to developmental, neurological (e.g., stroke) or other disorders including head trauma, or patients with dementia or epilepsy.
- 3. Severe movement disorders
 - Leading to cognitive impairment (e.g. Parkinson's dementia), or
 - Interfering with the efficacy assessments, or
 - Due to antipsychotic treatment that cannot be controlled with low dose anticholinergic treatment (equal to maximum 1 mg benztropine twice daily). Table of relevant medications and their equivalencies will be provided as a part of ISF
- 4. Any suicidal behavior in the past 1-year prior to screening and during the screening period.
- 5. Suicidal ideation of type 5 in the C-SSRS (i.e. active suicidal thought with plan and intent) in the past 3 months prior to screening and up to and including Visit 2.
 - Patients with Suicidal Ideation type 4 in the C-SSRS (i.e. active suicidal thought with intent but without specific plan), within 3 months prior to screening and up to and including visit 2, can be randomized in the study, if assessed and documented by a licensed mental health professional that there is no immediate risk of suicide.
- 6. History of moderate or severe substance use disorder (other than caffeine and nicotine), as defined in DSM-5 within the last 12 months prior to informed consent.
- 7. Positive urine drug screen at Visit 1 based on central lab test. For a list of drugs assessed in the urine drug screen, please refer to Table 5.2.3:1.
- 8. Patients who were treated with any of the following within 6 months prior to randomization:
 - Clozapine
 - Stimulants (e.g. methylphenidate, dextroamphetamine, modafinil)
 - Ketamine or esketamine
 - Electroconvulsive therapy (ECT) or modified ECT
- 9. Participation in any investigational psychoactive drug trial (both industry/ academic) in last 6 months, and 30 days or 5 half-lives for no-psychoactive drug trial, prior to randomization.
- 10. Patients who were previously treated with Iclepertin.
- 11. Patients who are treated with any of the following within the last 35 days prior to randomization¹:
 - Strong or moderate CYP3A4 inhibitors including grapefruit juice

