The C-SSRS is a semi-structured, investigator-rated interview, developed by clinical experts in cooperation with the FDA, assessing both suicidal behavior and suicidal ideation. It does not give a global score, but provides some categorical and some severity information specifically for behavior and ideation.

The computer-automated C-SSRS interview may be administered using a tablet device.

Patients who do not have suicidal behavior or ideation will answer a limited number of questions and will usually complete the assessment in about 3 minutes. Patients with significant suicidal ideation or behavior may require up to 10 minutes to answer all relevant questions. This assessment should be conducted early in the visit. At the conclusion of each assessment, the site will have access to the C-SSRS results. The results include the findings for suicidal ideation, intensity of ideation, suicidal behavior, and lethality / medical damage (for actual suicide attempts only).

The C-SSRS has been widely used in large multinational clinical trials. The C-SSRS will be administered first at screening (Visit 1) (using the 'Baseline / Screening' version) with the aim to exclude patients with active moderate or severe symptomatology within a specified time prior to screening. The life time history of suicidal ideation and behavior will also be recorded.

After screening (Visit 1) the assessment 'since last visit' will be performed at each clinic visit ('Since Last Visit version'). The investigator is to review/ consider the C-SSRS results for plausibility and clinical relevance. Doubtful results may be repeated or results may be validated by a consulting psychiatrist. If there is a confirmed positive report of suicidal behavior or suicidal ideation type 4 or 5 after start of trial, the investigator is to immediately interview the patient during the clinic visit (if the investigator did not administer the C-SSRS leading to the positive report), and/ or is to consult a psychiatrist if considered necessary.

For any positive suicidal ideation (type 1 to 5) or suicidal behavior, the rater must document additional details in the comment fields in the C-SSRS in Pathway.

If there is any new suicidality or increase in suicidality, please comment on the clinical significance and any additional follow-up actions that may be performed in the eCRF.

Page 55 of 112

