6.2.3.1 Randomization (Visit 2)

- At the start of Visit 2, the investigator or designee should ensure that all Visit 1 and Visit 1a procedures have been successfully completed
- The MCCB should be performed before any other efficacy assessment.
- Study procedures for Visit 2 can be split into 2 sequential days, in which case:
 - o The MCCB and VRFCAT must be performed on the first day.
 - The remaining assessments can be done per the convenience of the patient and site, either on day 1 or day 2.
 - To reduce burden on the study partner, it is recommended to perform the and the SCoRS on the same day.
 - o In case of a split visit, the second day will be the day of first study drug intake.
- For patients who have signed the optional Biobanking consent form, biobanking (plasma and serum) samples should be collected before the intake of the first dose of study medication (refer to Section 5.5.1). The DNA sample may be collected at visit 2 or at another visit as long as the biobanking consent is has not been revoked.
- The MCCB overall T-score from the visit 1 (screening) is required to randomize the patient at visit 2.
 - In case the screening MCCB T-score is not available at visit 2, site may postpone this visit by maximum of 2 weeks.
- Patient eligibility must be confirmed before the patient is randomized in the IRT. Intake of the study medication must be done after the patient has completed all of the other visit 2 assessments.
- First intake of study medication will be done on site using the AiCure medication adherence monitoring app and under supervision by delegated trial staff.
- Two medication kits will be dispensed at visit 2. These kits will contain sufficient trial drug for 28 days (21 treatment days plus 7 days reserve). For further information refer to Section 4.1.4.
- At each clinic visit, patients should be reminded not to take study medication at home on the morning of the visit. At each visit, patient will take medication at the clinic using AiCure under supervision by trial staff.

6.2.3.2 Visit 3 to Visit 10

- blood samples will be collected during the treatment period as per the Flow chart.
 Refer to section 5.3 and Appendix 10.1 for more details.
- Patients should be instructed to bring all trial medication (used and unused kits/packaging including blisters) with them to these clinic visits.
- At each visit, the patient will receive a new supply of study medication, as allocated by the IRT system.

c33087946-03

Clinical Trial Protocol

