## 4. CHANGES IN THE PLANNED ANALYSIS OF THE STUDY

For the further endpoint of change from screening Visit 1a in PRECIS individual items and domain scores at Week 24, only the PRECIS domain scores will be analyzed, and the PRECIS individual items will not be analyzed.

Definition of baseline for the assessments of efficacy, and C-SSRS will include assessments up to but no later than the day of the first administration of study medication.

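### The C-SSRS baseline in SAP 6.7 is normally a since-last-visit form covering about 7–14 days, so ideation recorded only at Visit 1 or 1a drops out of the baseline value

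*SAP*

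**What the plan says.** SAP 6.7 sets the rule: "For assessments of efficacy, and C-SSRS, baseline will be defined as the last available assessment performed at or before randomization (Visit 2"), with the day of first dosing as the latest permitted date. Earlier forms are a fallback only: "Assessments done at Visit 1 or Visit 1a can be used as baseline if Visit 2 assessment is not planned, not available, or invalid". SAP Section 4 lists this definition among the changes to the planned analysis: "Definition of baseline for the assessments of efficacy, and C-SSRS will include assessments up to but no later than the day of the first administration". That entry settles the cut-off day. It does not discuss which C-SSRS version supplies the value.

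The protocol's flow chart schedules the C-SSRS at Visits 1, 1a and 2 and at every later visit. Protocol 5.2 assigns the baseline/screening version to Visit 1 and adds that "The life time history of suicidal ideation and behavior will also be recorded". From then on, "After screening (Visit 1) the assessment 'since last visit' will be performed at each clinic visit".

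On eligibility, exclusion criterion 5 in protocol 3.3.3 bars recent type 5 ideation. Patients with type 4 ideation "within 3 months prior to screening and up to and including visit 2, can be randomized in the study", provided that a licensed professional documents no immediate risk. Types 1 to 3 are not excluded. Criterion 4 bars suicidal behaviour in the year before screening and during screening.

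**The concern.** Taking the last value before dosing suits a point measurement, where a later reading supersedes an earlier one. It does not suit an instrument in which each form reports a separate interval. There, choosing the last form discards what the earlier forms reported. A patient with type 4 ideation two months before screening, or type 2 ideation reported at Visit 1, can have a clean Visit 2 form and so a baseline of no ideation.

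What is at stake is how a safety display is read. Protocol Table 1.4.2:1 names suicidality as a risk and describes ideation and behaviour as common in this population. If on-treatment C-SSRS results are set against the SAP baseline, recurrence of recent ideation and genuine first onset fall into the same cell. Types 1 to 3 are the most exposed: under protocol 5.2.6.1.4 they become adverse events only if the investigator judges them so, which leaves the C-SSRS summaries as their only systematic record.

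**Working it through.** The plan gives no figure to reproduce. The check is which form becomes the baseline, and how much time it covers.

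**Inputs**
- Visit 1 window: Day -35 to -28; Visit 1a window: Day -14 to -7 (protocol flow chart).
- Forms: baseline/screening version at Visit 1, since-last-visit version from Visit 1a on (protocol 5.2).
- Visit 2 can slip if the screening MCCB score is late: "site may postpone this visit by maximum of 2 weeks" (protocol 6.2.3.1).
- Treatment period: 26 × 7 = 182 days. On-treatment visits are 21 days apart up to Visit 10, then 14 days to Visit 11 (flow chart).

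**Step 1: which form.** The C-SSRS is planned at Visit 2, so the fallback applies only when that form is unavailable or invalid. The usual baseline is the Visit 2 since-last-visit form.

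**Step 2: its look-back.** Counting from Visit 2, look-back = time since Visit 1a = 7 to 14 days. With Visit 1a at Day -14, a full two-week postponement and no repeat of Visit 1a, it is 14 + 14 = 28 days. An unscheduled C-SSRS in between would shorten it.

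**Step 3: share of screening covered.** Without postponement, the share of the Visit 1 to Visit 2 period is between 7/35 = 20% and 14/28 = 50%. The time before Visit 1 is not covered at all, and that is where the history collected at Visit 1 lies.

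**Step 4: comparison with the on-treatment record.** The mismatch depends on the display:
- Whole treatment period against the baseline form: 182/14 = 13 to 182/7 = 26 times as long.
- One three-weekly form against the baseline form: 21/14 = 1.5 to 21/7 = 3 times as long.

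The text available does not say which display is planned.

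**Step 5: what is lost.** For ideation, the baseline value omits any type recorded only at Visit 1 or 1a, including the type 4 ideation that criterion 5 admits. For behaviour the loss is narrower. Criterion 4 excludes patients with behaviour in the past year or during screening, so in correctly enrolled patients what falls outside the baseline is behaviour more than a year old, which belongs with lifetime history.

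**The case against.** The strongest objection is that the harm needs a comparison the documents do not spell out. Protocol 7.2.5 plans descriptive summaries of the C-SSRS, and no text available defines new, worsened or treatment-emergent ideation. Parts of the SAP are not shown (for example Tables 6.7: 4 to 6.7: 6), so such a rule, or a display of prior history, may exist there. This stands. A reader might infer that the SAP counts recurrent ideation as new; the documents do not say so. They do set a C-SSRS baseline deliberately, and protocol 7.2.5 says that other safety-relevant data will be assessed for change from pre-treatment findings. It is therefore reasonable to ask which records serve as the reference.

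A reader might also infer that screening ideation is ignored. It is not: it is recorded, it drives eligibility, and it can serve as baseline when Visit 2 fails. It is absent only from the usual baseline value.

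Nor are patient protection and serious-event reporting affected. Protocol 5.2.6.1.4 makes every type 4 or 5 report and all behaviour an SAE, and the withdrawal criterion in protocol 3.3.4.2 makes no reference to baseline.

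A further tempting reading is that the rule favours one arm. It is identical in both. An equal number of recurrences per patient added to each arm pulls a risk ratio toward 1 and leaves the risk difference unchanged.

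Finally, a pooled reference has its own cost: recurrence on drug at or below the earlier severity would no longer be labelled new or worsened, which is the less cautious direction for safety. That is fair, and the fix has to answer it.

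**Conclusion.** The point holds as a minor one. The stated C-SSRS baseline is normally a form covering about 7 to 14 days (up to about 28 with postponement), and it leaves out ideation reported only on earlier pre-treatment forms. Any summary of new onset or worsening built on it would mix recurrence with first onset in both arms alike.

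This rests on a valid Visit 2 form, on Visit 1a taking place in its window, and on the baseline being used as a reference at all. The documents give no prevalence of recent ideation, so the number of patients affected cannot be estimated. No hypothesis test, SAE report or withdrawal decision depends on it.

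**What to change.** In SAP 6.7, take the C-SSRS out of the last-available-assessment rule. The section already gives the MCCB a rule of its own, so a second exception fits.

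- Define the C-SSRS pre-treatment reference as the most severe ideation category, and any behaviour, across Visit 1 (recent recall period, with its length stated), Visit 1a and Visit 2.
- Show lifetime history separately.
- Use this reference for any summary of new or worsened ideation or behaviour, and state the definition of each.
- Also tabulate all on-treatment ideation and behaviour by arm regardless of baseline, so that recurrence at or below earlier severity stays visible.

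The cost is a few sentences in the SAP, a small change to the derivation and one extra table. All the forms are already collected, so no site procedure changes.

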Safety Laboratory tests ³	X		X		X		X		X	X^H	X	X	X		(X)		X		X	
PK Sample ⁴				X	X		X		X			X	X		X					
Bio-banking (optional) ⁵			X									X	X							
Speech sampling (optional) ⁶		X				X					X									
M.I.N.I. ⁷	X		X																	
In-/exclusion criteria	X		X																	
Randomization			X																	
AiCure training ⁸	X	(X)	X																	
AiCure review		X	X	X	X	X	X	X	X	X	X	X	X							
Contact IRT	X		X	X	X	X	X	X	X	X	X	X	X						X	
Duplicate patient check	X																			
(re)Dispense & administer trial drug at site ⁹			X	X	X	X	X	X	X	X	X									
IMP Compliance check				X	X	X	X	X	X	X	X	X	X							
Termination of trial drug												X	X							
MCCB	X		X				X					X	X							
VRFCAT	X		X				X					X	X							
PCRS & SCoRS ²⁰	X		X				X					X	X							
Tower of London	X		X									X	X							
		X	X				X				X	X	X		X		X		X	

Page 7 of 112

Proprietary confidential information © 2023 Boehringer Ingelheim International GmbH or one or more of its affiliated companies

FLOW CHART (con't)

Trial Periods and Procedures	Screening	g Period ¹				F	Rando	mized	Treat	ment l	Period	l			Sat	fety Follo	w-up Perio	od ¹⁸		End of Study
Visit	1	1a	2	3	4	5	6	7	8	9	10	EOT/11 ¹⁶	eEOT ¹⁷	Follow- up 1	Follow- up 2	Follow- up 3	Follow- up 4	Follow- up 5	Follow- up 6 ¹⁹	EOS
Weeks	Scree	ning	0	3	6	9	12	15	18	21	24	26	NA							
Days from first randomized treatment	-35 1		1	22	43	64	85	106	127	148	169	183	NA	EOT or eEOT + 7	EOT or eEOT +14	EOT or eEOT +17	EOT or eEOT +21	EOT or eEOT +24	EOT or eEOT + 28	
Clinic (on-site) visit	X	X	X	X	X	X	X	X	X	X	X	X	X		X		X		X	
Visit time window (days)	-35 to -28	-14 to -7	N/A	±3	±3	±3	±3	±3	±3	±3	±3	±3	NA	±1	±1	±1	±1	±1	+7	
PRECIS ¹⁰		X						X			X		X							
Adverse events ¹¹	X	X	X	X	X	X	X	X	X	X	X	X	X	X	X	X	X	X	X	
		X										X	X							
Concomitant therapy	X	X	X	X	X	X	X	X	X	X	X	X	X	X	X	X	X	X	X	
Substance use ¹²	X		X				X					X	X							
C-SSRS ²¹	X	X	X	X	X	X	X	X	X	X	X	X	X	X	X	X	X	X	X	
SAS/AIMS/BARS		X			X			X			X	X	X							
Physician withdrawal checklist ¹³											X		X	X	X	X	X	X	X	
Patient Participation Completion 14																				X
Duration in hours ¹⁵	7	3	6.5	1	2	2	4.5	2	2.5	1	3	6.5	7	0.5	2	0.5	3	0.5	3	

(X) Optional assessments at discretion of investigator

¹The screening period may take up to 35 days with 2 visits. At the second screening visit, urine drug screen may be repeated at discretion of investigators (X), if needed.

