2. TRIAL OBJECTIVES AND ENDPOINTS

2.1 MAIN OBJECTIVES, PRIMARY AND SECONDARY ENDPOINTS

2.1.1 Main objectives

The primary objective of this phase III pivotal trial in CIAS is to assess the efficacy in improving cognitive impairment using MCCB in patients with schizophrenia treated for 26 weeks with Iclepertin 10mg as compared with placebo.

The key secondary objective is to assess the efficacy in daily functioning of 26-week treatment with Iclepertin 10mg as compared with placebo in terms of Schizophrenia Cognition Rating Scale (SCoRS) and Virtual Reality Functional Capacity Assessment Tool (VRFCAT).

The secondary objectives are to assess the efficacy in improving reasoning and problem solving and patients' experience of cognitive impairment associated with their disease.

Patients will be required to be on stable antipsychotic treatment at the time of inclusion.

The primary treatment effect of interest is defined in the primary estimand framework as specified in detail in Section 7. All efforts will be taken to continue to collect efficacy data at planned visits after patients discontinued trial treatment following an intercurrent event. For patients who discontinued trial treatment after intercurrent events that will be handled by the treatment policy approach, these observed off-treatment data will be included in the primary analysis. For patients who discontinued trial treatment after other intercurrent events that will not be handled by the treatment policy approach, these observed off-treatment data will be censored and excluded from the primary analysis.

In summary, the primary treatment effect of interest is the effect obtained at the primary time point if patients had stayed on the treatment, i.e. taking the trial medication for the full treatment duration while allowing the following intercurrent events: change in concomitant medications or background non-pharmacological therapy, change in study partner, and treatment interruption or discontinuation due to exacerbation, an acute episode, adverse events (AEs) that are considered drug related and protocol-defined drug withdrawal.

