#### 5.2.2 Secondary endpoint(s)

[figure not shown]
The other secondary endpoints are:

[figure not shown]
- Change from baseline in the T-score of the number of correct responses on Tower of London (ToL) at Week 26
- Change from screening Visit 1a in Patient Reported Experience of Cognitive Impairment in Schizophrenia (PRECIS) total score at Week 24

A higher T-score in ToL indicates a better outcome. A lower score in PRECIS corresponds to a better patient experience.

The endpoints will be used as defined in CTP Section 5.

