#### 6.3 INTERCURRENT EVENTS

Definition and technical specification of protocol defined intercurrent events (ICEs) are listed in Table 6.3: 1. In general, when handled under the hypothetical approach, data collected during the off-treatment period of an ICE will be considered irrelevant to the estimand and excluded from the analysis. While off-treatment data will be excluded, the patient will still be

considered as on-treatment (hypothetically) from an analysis perspective by the statistical models, and during any imputations.

For an ICE of temporary treatment discontinuation or interruptions, the off-treatment period spans from the last treatment administration prior to the interruption + REP to the restart of the study medication. For an ICE of early permanent treatment discontinuation, the off-treatment period starts from the last treatment administration + REP. Figure 6.3: 1 illustrates the on-/off-treatment status after each type of ICEs. When there is more than one ICE of early permanent treatment discontinuation, any treatment policy ICE take precedence in data and analysis handling over any hypothetical ICE.

ICEs of change in concomitant therapies and other ICEs will always be considered as part of the treatment policy in the primary and all supplementary estimands. ICEs of this category will not affect the on-/off- treatment status which is only determined by changes in the study medication. These ICEs will be listed and summarized descriptively but will not be explicitly accounted for in the inferential analysis of efficacy.

Table 6.3: 1 Definition and technical specification of intercurrent events

[figure not shown]
Type of Intercurrent Event	Definition and Documentary Sources	Handling under the Primary Estimand
Temporary Tr	reatment Discontinuations or Interruption	ons
Exacerbation or acute episode of schizophrenia resulting in interruption of treatment	Identified from data collected in the Temporary Trial Treatment Discontinuation and Adverse Event pages of the CRF:  - Temporary discontinuation of trial treatment reported with reason being "Adverse Event", and  - AE category reported as "Schizophrenia Relapse" or MedDRA preferred term coded as "Schizophrenia"	Treatment policy

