# 7.5.2 (Other) Secondary endpoint analysis

For the secondary efficacy endpoints of change from screening to Week 24 in PRECIS total score and change from baseline to Week 26 in Tower of London number of correct responses T-score, the same strategy for handling the intercurrent events in the primary analysis under the primary estimand will be applied.

For change from screening to Week 24 in PRECIS total score, the primary analysis will be a restricted maximum likelihood (REML) based approach using the same primary analysis model of MMRM specified in Section 7.4.1, but with the baseline covariate replaced by the screening PRECIS total score. The same subgroup analyses as planned for the primary efficacy endpoint in Section 7.4.3 will also be conducted for PRECIS total score.

For change from baseline to Week 26 in the T-score of number of correct responses on Tower of London, an analysis of covariance (ANCOVA) model including treatment, stratification factor of screening MCCB overall composite T-score (<30, ≥30), and baseline number of correct responses on Tower of London T-score will be fitted to the data.

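### The Tower of London Week 26 window opens on Day 2, so an early end-of-treatment score can be analysed as the Week 26 outcome

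*SAP*

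**What the plan says.** - **Endpoint.** SAP 5.2.2 defines it as "Change from baseline in the T-score of the number of correct responses on Tower of London (ToL) at Week 26".
- **Schedule.** In the protocol Flow Chart the "Tower of London" row is marked at Visits 1 and 2, EOT/Visit 11 and eEOT only. Protocol 6.2.3.4 requires the eEOT visit within 7 days of the last dose.
- **Window.** "Table 6.7: 3 Analysis visit windows for Tower of London" has a baseline row (Day 1 or earlier) and one post-baseline row: Visit 11, Week 26, planned Day 183, actual Day 2 or later.
- **Which scores can be mapped.** Under SAP 6.7, "off-treatment data will be included into mapping consideration only when the associated ICE is handled under the treatment policy approach". For a permanent stop, SAP 6.3 says that "the off-treatment period starts from the last treatment administration + REP"; the residual effect period (REP) is 12 days (SAP 6.1).
- **Choice among several scores.** The one "performed closest to the planned day will be selected for analyses".
- **Strategy and model.** For ToL, SAP 7.5.2 states that "the same strategy for handling the intercurrent events in the primary analysis under the primary estimand will be applied". It then fits an ANCOVA with treatment, stratum and baseline ToL to the single mapped value.
- **Other tested endpoints.** Table 6.7: 1 (MCCB, VRFCAT, SCoRS) counts a score as Week 26 only from Day 127. Table 6.7: 2 uses the same lower bound for PRECIS at Week 24.

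**The concern.** The ToL window sets no limit on how early a Week 26 score may be. For some patients who stop treatment, the rule acts as a carry-forward of the last on-treatment value, without being named as one. The hypothetical part of the estimand (Protocol 2.1.1) is different: "the primary treatment effect of interest is the effect obtained at the primary time point if patients had stayed on the treatment". A score taken after a few weeks of treatment does not estimate that.

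MCCB, VRFCAT and SCoRS have a Week 12 visit to hold earlier scores. ToL has none, so an early ToL score has no valid analysis visit and should be missing at Week 26.

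ToL is H4 in Family 3 of the gatekeeping procedure, so it is under type I error control. Its result would be reported as a Week 26 effect while mixing scores taken after anything from days to 26 weeks of treatment, weighted by the dropout pattern. The expected consequence is some dilution towards the null. Bias in either direction is possible if early stopping differs between arms, but the documents give nothing to size that.

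**Working it through.** **Rule check on one patient.** Last dose Day 40, eEOT Day 45, Visit 11 on Day 183. Off-treatment status starts at Day 40 + 12 = Day 52, so the Day 45 score is on-treatment.

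- Hypothetical-strategy stop: the Day 183 score is excluded and the Day 45 score is analysed as Week 26, which is 183 − 45 = 138 days early. The MCCB from the same visit maps to Week 12.
- Treatment-policy stop: the Day 183 score is used if it exists; otherwise the Day 45 score is used.
- Completers keep their true Week 26 score.

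**The plan's own figure.** Protocol Table 7.5: 1 gives 75.2% gatekept power for ToL in Scenario #1 (effect 0.275, 220 evaluable per arm). A simulation of the same procedure gives 75.6%, so the stated figure reproduces. It assumes that every evaluable value carries the full Week 26 effect.

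**Size: inputs**

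- d = 0.35, early termination (mid-point of the 30–40% in Protocol 7.5).
- r = 0.375, treatment-policy stoppers with a Visit 11 ToL (mid-point of the 25–50% with outcomes after termination in Protocol 7.5, which names no visit; applying it to Visit 11 is an assumption).
- h = 0.5, share of stops that are hypothetical-strategy (assumption).
- a = 0.5, eEOT ToL completion among the remaining stoppers (assumption).
- Stop day uniform over Days 2–182 (assumption), with the eEOT score placed on the stop day.

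**Share of early scores**

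- True Week 26 values: (1 − d) + d(1 − h)r = 0.65 + 0.35 × 0.5 × 0.375 = 0.716.
- eEOT values: d·a·[h + (1 − h)(1 − r)] = 0.175 × (0.5 + 0.3125) = 0.142.
- Share: 0.142 / (0.716 + 0.142) = 0.166.
- Per arm (× 293): 251 values, of which 42 are eEOT scores.
- Before Day 127: 125 of 181 days = 0.691, so 0.691 × 0.166 ≈ 0.11, or 29 values.

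**Dilution**

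- Effect linear to Day 183: mean shortfall 1 − 92/183 = 0.497; dilution 0.166 × 0.497 = 0.082.
- Effect linear to Day 85, then flat: mean shortfall 0.227; dilution 0.166 × 0.227 = 0.038.

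**Range.** Grid: d 0.30/0.40, h 0.3/0.5/0.8, r 0.25/0.50, a 0.25/0.50.

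| Quantity | Mid-case | Range |
|---|---|---|
| eEOT share of Week 26 values | 17% | 6–23% |
| Before Day 127 | 11% | 4–16% |
| Dilution, linear | 8% | 3–12% |
| Dilution, plateau | 4% | 1–5% |

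Two variations on the mid-case:

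- If only 25% of hypothetical-strategy stoppers have an eEOT ToL, the share is 12%, 8% predate Day 127, and dilution is 6% (linear) or 3% (plateau).
- If every eEOT falls 7 days after the stop, linear dilution is 7.6% and plateau dilution 3.2%.

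**With the window from Day 127, mid-case.** eEOT values kept: 0.142 × 56/181 = 0.044. Values per arm: 293 × (0.716 + 0.044) ≈ 223. Linear dilution is 0.9% (grid maximum 1.3%).

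**Stand-alone power** at effect 0.275, one-sided 0.025, normal approximation:

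| Window | n per arm | Linear | Plateau |
|---|---|---|---|
| Day 2 onward | 251 | 0.808 | 0.843 |
| Day 127 onward | 223 | 0.820 | 0.827 |

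**The case against.** - **The consequence is small.** Power barely moves, and whether the change helps or hurts depends on the shape of the effect over time, which the documents do not give. This stands. The case rests on what is being estimated, not on power.
- **The size is not fixed by the documents.** If 37.5% were all stoppers with any usable ToL, the eEOT values would be 0.35 × 0.375 − 0.0656 = 0.0656. The share would be 0.0656 / 0.781 = 8.4%, with dilution of about 4% or 2%. That reading is possible and lies inside the range above. ToL is also outside the minimum set encouraged at eEOT, and withdrawal of consent ends assessments, so near-complete eEOT ToL is unlikely.
- **Dropping early scores has its own cost.** Stops for perceived lack of efficacy are hypothetical-strategy events. A complete-case ANCOVA would assume that those patients resemble others with the same treatment, stratum and baseline. This partly stands. The primary analysis also assumes missing at random, but for MCCB the Week 12 visit supports it, and ToL has no such visit. It is a reason to keep the present mapping as a supplementary analysis.
- **The protocol treats on-policy measurements as relevant, and wide windows are this SAP's convention.** Protocol Section 7 does say the former, but relevance does not turn a Day 45 score into a Week 26 outcome. A Day 127 bound still admits scores up to 56 days early. Its merit is that the other four tested endpoints already use it for their final visit.
- **Redacted text might qualify the rule.** This cannot be excluded, but the visible ToL row is complete and no visible text limits it.

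**Conclusion.** The concern holds. The visible rules, read together, let an eEOT ToL score from any day after baseline be analysed as Week 26 after a hypothetical-strategy stop, or after a treatment-policy stop with no Visit 11 ToL. That the mapping departs from the endpoint and from the estimand applied to ToL follows from the text alone.

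Its size does not. The mid-case of 17% early scores and 4–8% dilution depends on the split of stops by strategy, eEOT completion, stop timing and the shape of the effect, none of which the documents give. On any of the assumptions tried it is a modest problem on a Family 3 endpoint, and trial success on MCCB is untouched. It should be corrected because the endpoint is formally tested and the correction costs little.

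**What to change.** Before unblinding, change the ToL Week 26 window in Table 6.7: 3 from Day 2 onward to Day 127 onward, matching Table 6.7: 1. Treat earlier ToL scores as missing at Week 26 and keep the pre-specified ANCOVA under missing at random. Retain the present mapping as a supplementary analysis, labelled as carrying the last on-treatment score forward.

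If imputation is wanted as a sensitivity analysis, base it on baseline ToL and the Week 12 values of MCCB, VRFCAT and SCoRS. Do not base it on eEOT ToL: completers have no intermediate ToL from which to estimate that relation.

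The cost is one table row and one extra analysis. Fewer ToL values are analysed: about 223 instead of 251 per arm in the mid-case (11% fewer; 4–16% over the range). That leaves 1 − 223/293 = 24% missing, in line with the 25% correction in Protocol 7.5 and still above the 220 evaluable per arm that it assumes.
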